10.0 CROSS-OVER

Subjects randomized to Group B may cross-over to Group A after discussion with, and approval from the Gradalis medical monitor or authorized designee.

Within 6 weeks of second relapse or progression and if alternative therapy has not been given since EOT, subjects randomized to Group B, will be allowed to cross-over to receive single agent Vigil every 21 days following End of Treatment assessment. Subjects who cross-over may receive up to 12 doses of Vigil depending upon the quantity of Vigil manufactured. After the Group B EOT assessment, the subject will start "cross-over" from Assessments During Treatment onward. Vigil and all assessments will occur on Day 1 of each cycle.

Cross-over must occur within 2 years of End of Treatment assessments of Group B enrollment. Subjects who progress \geq 8 weeks post EOT assessment must re-screen and if they qualify will start "cross-over" from Assessments During Treatment onward. Eligibility criteria for cross-over subjects are listed below.

10.1 Inclusion Criteria for Cross-Over

Subjects will be eligible for cross-over, if they meet all of the following criteria:

- 1. Evidence of radiologic disease progression by RECIST 1.1 after enrollment into Group B.
- 2. Successful manufacturing of at least 4 vials of Vigil.
- 3. Karnofsky performance status (KPS) / Lansky performance status (LS) ≥70%.
- 4. Normal organ and marrow function as defined below:

Absolute granulocyte count	≥1,000/mm³	
Absolute lymphocyte count	≥400/mm³	
Platelets	≥75,000/mm³	
Total bilirubin	≤ institutional upper limit of normal	
AST(SGOT)/ALT(SGPT)	≤2x institutional upper limit of normal	
Creatinine	<1.5 mg/dL	

*documented Gilbert's syndrome may be considered after medical monitor review

- 5. Subject has recovered to CTCAE Grade 1 (except for parameters noted in Item 4, above) or better from all adverse events associated with prior therapy or surgery. Preexisting motor, sensory neurologic pathology or symptoms, or dermatologic toxicities must be recovered to CTCAE Grade 2 or better.
- 6. If female of childbearing potential, has a negative urine or serum pregnancy test. If the urine test is positive or cannot be confirmed as negative, a negative serum test will be required for study entry.
- 7. Ability to understand and the willingness to sign a written informed protocol specific consent or a parental/guardian informed consent and pediatric assent when appropriate.

10.2 Exclusion Criteria for Cross-Over

In addition to the Procurement and Study Enrollment exclusion criteria, Subjects will NOT be eligible for cross-over if meeting any of the following criteria:

- 1. With the exception of irinotecan and temozolomide while on study, any anti-neoplastic therapy between tissue procurement for Vigil manufacture and start of study therapy.
- 2. Live vaccine used for the prevention of infectious disease administered < 30 days prior to the start of study therapy.

11.0 CONDUCT OF THE STUDY

11.1 Ethics and Regulatory Considerations

This study must have the approval of a properly constituted Institutional Review Board (IRB) or Independent Ethics Committee (IEC). Before the investigational drug is shipped to the investigator, the investigator will provide Gradalis, Inc. with a copy of the IRB or IEC approval letter stating that the study protocol and informed consent form have been reviewed and approved.

11.2 IRB

This trial can be undertaken only after review and full approval of the protocol and an Informed Consent Form has been obtained from a properly constituted IRB. This written approval must be dated and it must clearly identify the protocol, any amendments, the Informed Consent Form, and any applicable recruiting materials and subject compensation programs approved.

The decision concerning the conduct of the study will be made in writing to the sponsor. Copies of this decision and of all IRB correspondence will be kept on file at the study site; copies will be provided to the Sponsor Office.

During the trial, the PI is required to send various documents to the IRB for review:

- All protocol amendments and Informed Consent Form revisions.
- Reports of Serious Adverse Events.

The PI provides Gradalis, Inc. with the necessary assurance that an IRB is responsible for the initial and continuing review and approval of the proposed clinical study in accordance with 21 CFR 312.60. At least once a year, the IRB will be asked to review and re-approve the clinical trial protocol; the request must be documented in writing. At the end of the trial, the PI will notify the IRB that the trial has been completed.

11.3 Written Informed Consent

The informed consent document should meet the requirements of the latest version of the Declaration of Helsinki and any applicable regulations and guidelines. It must be approved by an IRB or IEC.

Prior to entry into the trial and before any protocol-required procedures are performed, the Investigator must explain the nature of the trial, its intended purpose, and the implications of participation to potential subjects or to their legal representatives. They will be told about the possible risks and benefits, and the possible adverse experiences. They will be informed that subjects' participation is voluntary, and that they may withdraw consent to participate at any time. They will also be informed that if subjects choose not to participate in the trial alternative treatments are available; such refusal will not prejudice further treatment of their disease. Potential subjects or their legal representatives must be given the opportunity to ask questions about the trial protocol and the procedures involved.

Finally, each subject will be told that his or her records may be accessed by authorized personnel of Gradalis, Inc. and other authorized individuals without violating the subject's confidentiality, to the extent permitted by the applicable laws and/or regulations. By signing the written Informed Consent Form, the subject or his or her legal representative is authorizing such access. Following this explanation and prior to entry into the trial, the written, dated, and signed Informed Consent Form must be obtained from each subject or his or her legal representative; a copy will be given to the person signing the form.

11.4 Confidentiality of Records

The Investigator is required to retain, in a confidential manner, sufficient information on each subject (i.e., full name, current address, and social security number) so that the subject may be contacted by the FDA, Gradalis, Inc., or by their affiliates should the need arise.

11.5 Modification of Protocol

Any changes to this protocol that affect study objectives, study design, study procedures, patient population, or significant administrative procedures will require a formal amendment to the protocol. Any proposed protocol amendments must be sent in writing to the applicable IRB. Prior to implementation, an amendment must be approved by the Gradalis, Inc., and approved by the applicable IRB or IEC.

General administrative changes to the protocol are minor corrections and/or clarifications that do not affect the manner in which the study is to be conducted. Such administrative changes will be agreed upon by the Gradalis, Inc., and will be documented in a memorandum. The applicable IRB or IEC will be notified of administrative changes according to applicable IRB guidelines.

11.6 Protocol Questions and Deviations

When evaluating a potential patient or while a patient is on study, protocol questions can be directed to Gradalis via email or phone using the contact information provided in the Contact Information section of the Study Reference Manual.

11.7 Data Safety Monitoring Board

An independent data monitoring committee (IDMC) or Data Safety Monitoring Board (DSMB) will be established for this trial. Membership will include physicians with appropriate areas of expertise in the therapeutic areas of most interest. A charter will be developed to document their operational methods and timing of safety reviews.

12.0 EVALUATION OF TUMORS

12.1 Tumor Measurements and Response (RECIST 1.1)

Response and progression will also be evaluated in this study using the Response Evaluation Criteria in Solid Tumors (RECIST) Version 1.1. The guidelines are available online at: European Organization for Research and Treatment of Cancer (EORTC) RECIST Web page, https://www.eortc.be/Recist/documents/RECISTGuidelines.pdf.

Radiological images should be submitted to WorldCare upon receipt from the imaging facility for third party review.

13.0 DRUG INFORMATION

13.1 Vigil Investigational Product

Vigil is made up of irradiated autologous tumor cells which have been electroporated *ex vivo* with the Vigil plasmid designed to suppress expression of both the TGF β 1 and TGF β 2 proteins while simultaneously expressing rhGMCSF protein.

Vigil Production

The Vigil manufacturing process is identical to prior Vigil manufacturing (BB-IND 14205) (Maples 2010). Surgically excised tumor is collected in the surgical field and placed in 0.04mg/ml of gentamicin and sterile saline then packaged for transport to the manufacturing facility. The tumor is mechanically and enzymatically dissociated into a single cell suspension. The cells are counted and then transfected with the Vigil plasmid. The cells are incubated overnight to allow transcription of the Vigil plasmid. The following morning the cells are harvested, washed, and then irradiated at 10,000cGy in a standard Blood Bank irradiator. The irradiated cell suspension is then enumerated, aliquoted and frozen (1 x 10⁶ cells). The freeze media consists of 10% DMSO (dimethyl sulfoxide; Cryoserv USP; Bionichepharma US), 1% Human Serum Albumin (ABO Pharmaceuticals) in Plasma-Lyte A at pH 7.4 (Baxter). After

freezing the cells are stored in the vapor phase of liquid nitrogen until all release testing is completed, all necessary approvals are obtained and the patient is ready for treatment.

Safety Analysis

Vigil plasmid employed in the generation of this product has been tested for identity, sterility, purity and strength.

Irradiated Gene Modified Tumor Cells

To ensure safety, all gene-modified tumor cells to be used in Vigil administrations must be irradiated 10,000 cGy prior to freezing. This is the same irradiation process as for the TAG vaccine, BB-IND 13650 and prior vaccines (Belagenpumatucel-L and GVAX® published trial results and BB-IND 13401 and BB-IND 12118) (Kumar 2009, Maples PB 2009, Maples PB 2009). The selection of this radiation dose is based on the desire to utilize the lowest possible radiation dose for the transfected cells to optimize the level and duration of bifunctional shRNA^{furin} transcription and GMCSF protein production and maximize the safety of vaccine cell injections at the same time. In addition, investigators have demonstrated that irradiating cultured tumor cells of different histologic origins at 10,000 cGy completely arrests tumor colony formation.

Preparation

Reference the Study Reference Manual for preparation and handling information.

Vigil concentrate: 1.0×10^6 cells per injection in a volume of 1mL.

Route of administration: Intradermal injection

Storage and Shipping

Frozen, unopened vials are stored in the vapor phase of Liquid Nitrogen below -150° C at Gradalis. Each Vigil concentrate will be shipped individually in a portable liquid nitrogen tank. This shipping container will be able to sustain temperature fluctuations for up to 7 days. This will enable sufficient time to reach the different clinical site pharmacies.

Study medications are not expected to pose significant occupational safety risks to investigational staff under normal conditions of use and administration. However, precautions

should be taken to avoid direct contact with study medication. Biosafety Level 1 practices shall be employed with this study medication. Reference the Study Reference Manual.

14.0 ADVERSE EVENTS

14.1 Adverse Event and Serious Adverse Event Definitions

Adverse Event

An AE is any untoward medical occurrence in a patient or clinical investigation subject administered a pharmaceutical product and that does not necessarily have a causal relationship with this treatment. An AE can therefore be any unfavorable and unintended sign (including an abnormal laboratory finding), symptom, or disease temporally associated with the use of a medicinal (investigational) product, whether or not related to the medicinal (investigational) product.

Serious Adverse Event

An AE (experience) or reaction occurring at any dose should be classified as a serious adverse event (SAE) if any of the following occur:

- Initial or prolonged hospitalization (≥ 24 hours). This does not include hospitalizations which are part of routine medical practice.
- A life-threatening condition (i.e. an event in which the patient was at risk of death at the time of the event; it does not refer to an event which hypothetically might have caused death if it was more severe)
- Significant disability/incapacity (i.e. the AE resulted in a substantial disruption of the subject's ability to carry out normal life functions)
- Congenital anomaly/birth defect
- It does not meet any of the above serious criteria, but may jeopardize the subject or may require surgical or medical intervention to prevent one of the outcomes listed above.
- Death

Unexpected Adverse Event

An unexpected event is any AE that is not identified in nature, severity or frequency in the clinical Investigator's brochure or the drug package insert.

Grading Adverse Events

Adverse events (AEs) will be recorded throughout the trial. Toxicities and AEs will be graded and reported using the Common Toxicity Criteria for Adverse Events (CTCAE) Version 5. All AEs, regardless of severity, will be followed by the Treating Physician until resolution is satisfactory.

14.2 Attribution of Causality

The relationship of each event to treatment will be assessed by the Treating Physician and recorded on the CRF in the EDC.

14.3 Vigil Expected Side Effects

Tumor cell vaccines have been previously administered to patients with cancer. Side effects were minimal, the most frequent of which included local reactions at the site of injection. Potential adverse events are listed below.

Local skin reactions at the site of injection:

Erythema, tenderness, induration, urticaria/rash, pruritus.

Other expected adverse events:

Fever, myalgias/arthralgias, chills/rigors, nausea, fatigue, headache, thrombocytopenia and other cytopenias, hyperglycemia, vomiting, hypotension, infection at the immunization site.

In addition, there may also be a risk of autoimmune disease development, although to date no evidence of this has been seen in any vaccination study. There may also be worsening of tumor related symptoms secondary to immune mediated attack on patient's tumor.

14.4 Recording of an Adverse Event

Adverse events will be recorded for the duration of a subject's time on study: following procurement of the subject's tissue for tissue manufacture and for up to 30 days following the last administration of Vigil. All AEs, regardless of causal relationship are to be recorded in the eCRF and source documentation. Additional information about each event, such as treatment

required, eventual outcome, and whether or not therapy had to be interrupted or dosages reduced, will also be recorded on the eCRF.

Pre-existing conditions will be recorded at baseline on the Medical History Form. If a preexisting condition does not change, it does not have to be reported as an AE on subsequent cycles.

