Temozolomide / irinotecan: Per package inserts and institutional standards. A home supply of anti-emetic (e.g. ondansetron) is highly recommended to take before temozolomide and as needed. Also, a patient supply of an anti-diarrheal medication (e.g. loperamide) should be available after irinotecan for use as needed.

The patient should be educated with a study calendar indicating days to get chemotherapy and/or Vigil as well as supportive care medications and when Vigil is given.

Vigil Immunotherapy Transfer

All manufactured Vigil will be stored in the vapor phase of liquid nitrogen until ready for use. The site will contact Gradalis, Inc. when the study agent is needed for subject administration.

Gradalis will complete a Drug Transfer and Administration Form to release the subject vaccine. The clinic will sign off on the form upon receipt of the administration.

Please reference the Study Reference Manual for preparation and handling information.

Dose Modification for Vigil Toxicity

If > Grade 2 toxicity by NCI Common Toxicity Criteria (excluding Grade 3 injection site reactions) develops related to study treatment the Vigil dose will be reduced by 50% and continued.

Dose Modifications for temozolomide and irinotecan

Dose modifications for temozolomide, and irinotecan may be necessary for subject safety and should be carried out in accordance with the Investigator's standard of practice, the package inserts, and institutional standards. Please contact the sponsor regarding any dose modifications.

If irinotecan + temozolomide is administered beyond 12 cycles, it will be administered off study and no longer provided by Gradalis.

If irinotecan + temozolomide is discontinued, Vigil may be administered every 3 weeks until all manufactured product is exhausted or when disease progression is noted.

Study Regimen Delay

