- 8. Serum chemistries (creatinine, glucose, total protein, blood urea nitrogen (BUN), total carbon dioxide (CO2), albumin, total bilirubin, alkaline phosphatase, and aspartate transaminase (AST) and/or alanine transaminase (ALT)) and electrolytes (total calcium, chloride, potassium, sodium) must be performed.
- 9. Blood collection for immune function analysis (ELISPOT).
- 10. Plasma collection for immune function analysis (ctDNA).
- 11. Pregnancy test for those of childbearing potential.
- 12. Submission to Gradalis, Inc. of preferably 20 unstained tumor slides or tissue block for correlative immunohistochemistry assay. These slides should correlate with tumor procured for vaccine manufacture.

Assessments During Treatment

The following evaluations will be performed on Day 1 of each cycle (1 Cycle = 21 days \pm 3 days) (unless otherwise specified):

- 1. *A physical examination, including vital signs and body weight.
- 2. *A toxicity assessment (CTCAE v 5).
- 3. *Assessment of concomitant medications.
- 4. Radiological assessment of disease status with CT chest /abd/pelvis (MRI abd/pelvis may be substituted for CT abd/pelvis) every 6 weeks ± 7 days from Cycle 1 regardless of treatment arm assignment or treatment delay. The methods used for prestudy assessments (e.g., CT or MRI) should be used throughout the study. If possible, the same equipment should be used each time.
- 5. *A CBC with differential and platelet count.
- 6. *Serum chemistries (creatinine, glucose, total protein, blood urea nitrogen (BUN), total carbon dioxide (CO2), albumin, total bilirubin, alkaline phosphatase, and aspartate transaminase (AST) and/or alanine transaminase (ALT)) and electrolytes (total calcium, chloride, potassium, sodium).
- 7. Blood collection for immune function analysis (ELISPOT) on Day 1 (prior to chemotherapy administration) at Cycles 2, 4, and 6.
- 8. Plasma collection for immune function analysis (ctDNA) on Day 1 prior to chemotherapy administration at Cycles 2, 3, 4 and 6.
- 9. *Assessment of Karnofsky Performance Status or LS.
- 10. Group A and B participants: oral temozolomide 100 mg/m² daily (Days 1 5, total dose 500 mg/m²/cycle)
- 11. Group A and B participants: oral irinotecan 50 mg/m² daily (Days 1 5, total dose 250mg/m²/cycle)
- 12. Group A participants: Vigil 1.0 x 10⁶ cells/injection, intradermally on Day 15.
- 13. Cross-over Subjects: Vigil 1.0 x 10⁶ cells/injection, intradermally every 21 days

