- 14. For those randomized to Group A or in cross-over, Vigil administration. Day 16 post Vigil administration assessment of injection site. Instruct the subject on Day 15 to observe the injection site 24 hours after the product administration. (This may be conducted at home). Have the subject follow up with the clinic if an injection site reaction is present. Please note if the subject reports of any redness, swelling or other response. If the subject identifies any redness, and /or swelling, please ask the subject if it is feasible to take a photograph of the injection site. If photographing the injection site is possible, please instruct the subject to place a measuring tool (bulk supplies provided to the site) next to the injection site reaction in the picture, if feasible. The photograph may be provided to the clinic upon the next visit as a hard copy or electronic jpg image. Please instruct the participant to avoid capturing images that would identify the subject (i.e. face and head).
- 15. Submission of Next Generation Sequencing data, if available in medical records.

Subjects who are stable at the end of Cycle 4, with prior approval by the Sponsor may conduct evaluations denoted with an asterisk* on Day 15 of each cycle (1 Cycle = 21 days \pm 3 days) (unless otherwise specified).

Subjects who become child-bearing while on study will have a pregnancy test performed prior to their next dose. See Section 8.6.

End of Treatment Assessments

The following evaluations will be performed within 30 days after completion of the study regimen and / or within 30 days of disease progression (whichever event occurs first) (unless otherwise specified):

- 1. A physical examination, including vital signs and body weight.
- 2. Toxicity assessment (adverse events).
- 3. Assessment of concomitant medications taken.
- 4. Assessment of Karnofsky Performance Status/Lansky Performance Status
- 5. Radiological assessment of disease status with CT chest /abd/pelvis (MRI abd/pelvis may be substituted for CT abd/pelvis) within 45 days of the last injection or disease recurrence or progression
- 6. A CBC with differential and platelet count.
- 7. Serum chemistries (creatinine, glucose, total protein, blood urea nitrogen (BUN), total carbon dioxide (CO2), albumin, total bilirubin, alkaline phosphatase, and aspartate transaminase (AST) and/or alanine transaminase (ALT)) and electrolytes (total calcium, chloride, potassium, sodium).

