14.5 Serious Adverse Event Reporting

All SAEs will be reported to Gradalis, Inc. within 24 hours of notification by the site through email or facsimile. This includes any death from any cause following procurement of the subject's tissue for tissue manufacture and for up to 30 days following the last dose of the protocol study agent (Vigil).

The site will supply as much information as is available at the time of the initial notification (study number, patient initials, patient study number, onset date, relationship, patient demographics, event, dosing regimen of study agent) to:

Gradalis, Inc.			
[name]			
[contact]			
Direct: [contact]	[contact]		

Gradalis, Inc. will report adverse events to the FDA in compliance with 21 CFR 312.32.

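### AE recording (14.4) and death reporting (14.5) end 30 days after the last Vigil dose, so the window has no end for Group B subjects who do not cross over and can close before study chemotherapy ends in Group A

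*Protocol*

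**What the plan says.** Protocol 14.4 opens broadly, "Adverse events will be recorded for the duration of a subject's time on study", but after a colon spells that time out as running from tissue procurement and "for up to 30 days following the last administration of Vigil". Protocol 14.5 begins "All SAEs will be reported to Gradalis, Inc. within 24 hours of notification by the site", with no end date. Its next sentence brings in deaths from any cause, from procurement and "for up to 30 days following the last dose of the protocol study agent (Vigil").

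Other parts of the documents set wider or different limits:

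- Protocol 14.1: "Adverse events (AEs) will be recorded throughout the trial".
- Protocol 9.0 and Appendix B: a toxicity assessment on Day 1 of every cycle in both arms, and another at End of Treatment, "within 30 days after completion of the study regimen and / or within 30 days of disease progression", whichever comes first. The quarterly Response Follow-Up list contains no toxicity assessment.
- Protocol 15.1: the investigator notifies the sponsor of serious or unexpected AEs associated with study medication at any time after discontinuation.
- SAP 10.3: an event is treatment-emergent from the first dose until the subject terminates, withdraws from or completes the study.
- SAP 13.2: AEs are summarised as frequencies and percentages by treatment group.

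For exposure, Group B receives irinotecan and temozolomide only, with Vigil available by cross-over after progression (Protocol 10.0). Group A receives 4 to 12 Vigil doses, depending on how much could be manufactured. Chemotherapy has its own limit in 8.4.1: "If irinotecan + temozolomide is administered beyond 12 cycles, it will be administered off study".

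**The concern.** The recording window hangs on a drug that one arm is not randomised to receive and whose dose count in the other arm depends on manufacturing yield. A site that follows 14.4 literally has no stop date for a Group B subject who never crosses over. It could also stop entering AEs for a Group A subject with few doses who is still taking study chemotherapy. A site that follows 14.1 would keep recording.

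Two things are at stake. The first is completeness: non-serious AEs and deaths on study chemotherapy may fall outside the written window. The second is comparability: crude percentages depend on how long each subject is observed, and here that length would vary with arm, dose count, cross-over and site interpretation.

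**Working it through.** The documents state no figure for this window, so there is none to reproduce. The check is calendar arithmetic on the protocol's own schedule.

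**Inputs.** Cycle of 21 days (5.0). Vigil on Day 15 of each cycle, 4 to 12 doses (5.0, 8.4.1). Chemotherapy on Days 1 to 5, at most 12 cycles on study (8.4.1). Window of 30 days after the last Vigil dose (14.4). Assumptions: no delays, all 12 chemotherapy cycles given, day 1 is Cycle 1 Day 1.

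**Formulas.** For k Vigil doses:

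- last Vigil day = 21(k − 1) + 15
- window closes = last Vigil day + 30
- last on-study chemotherapy day = 21 × 11 + 5 = 236
- gap = 236 − window close

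For k = 4: 21 × 3 + 15 = 78; 78 + 30 = 108; 236 − 108 = 128 days.

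| Vigil doses | Last Vigil day | Window closes | Gap to last chemotherapy (days) | Chemotherapy cycles starting after close |
|---|---|---|---|---|
| 4 | 78 | 108 | 128 | 6 |
| 6 | 120 | 150 | 86 | 4 |
| 8 | 162 | 192 | 44 | 2 |
| 10 | 204 | 234 | 2 | 0 |
| 11 | 225 | 255 | none (19 days beyond) | 0 |
| 12 | 246 | 276 | none (40 days beyond) | 0 |

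With 4 doses, Day 108 is Day 3 of Cycle 6 (Cycle 6 starts on 21 × 5 + 1 = 106), and Cycles 7 to 12 start after the window has closed.

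**Against a common anchor.** With the protocol's own 30 days counted from the last dose of either treatment, a subject on 12 chemotherapy cycles is followed to Day 236 + 30 = 266, or to Day 276 with 12 Vigil doses. The present window falls short of that by 266 − 108 = 158 days at 4 doses, 266 − 192 = 74 at 8, 266 − 255 = 11 at 11, and 0 at 12.

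**Group B.** Without cross-over there is no Vigil date and the formula returns nothing. With cross-over, the window ends 30 days after the last cross-over dose, and cross-over may start up to 2 years after the End of Treatment assessments (10.0).

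**How often it could matter.** Taking the plan's control median PFS of 6 months (182.6 days) and hazard ratio of 0.45, and assuming exponential PFS, the proportion progression-free at Day 108 is 0.5^(108/182.6) = 66% in Group B and 0.5^(0.45 × 108/182.6) = 83% in Group A. Treatment beyond Day 108 would then be common. The documents do not give the distribution of dose counts, so the share of Group A affected cannot be computed.

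**The case against.** The strongest reply is that safety capture is already provided for in both arms. The opening words of 14.4 cover the whole time on study, 14.1 says the same, toxicity is assessed every cycle and at End of Treatment regardless of arm, and the SAP counts events to the end of participation. This stands as far as it goes: it would be wrong to infer that capture in Group B is undefined as a whole. What is missing there is the end of the recording period. The broad wording does not cure that, because 14.4 itself goes on to specify the narrower period.

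A reader might infer from 14.5 that SAE reporting as a whole stops 30 days after Vigil. The text does not support this. The duty to report all SAEs carries no end date; the Vigil limit sits in the sentence on deaths; and 15.1 adds later notification of associated serious or unexpected events. Reporting of non-fatal SAEs is therefore not clearly time-limited.

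A reader might also infer that the rule flatters the Vigil arm. That is not established. With few doses, Group A may be cut short; with 11 or 12 doses its window outlasts chemotherapy; and sites could under-collect in Group B for want of a date. Nor does Group B never receive Vigil, since cross-over subjects may have up to 12 doses.

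Finally, the Group A gap presumes that on-study chemotherapy continues after Vigil runs out. Section 8.4.1 limits chemotherapy by cycle number alone, but the Response Follow-Up text in 9.0 lists using up the vaccine among the reasons for study agent discontinuation that lead to quarterly follow-up. The documents are not clear on this, and those passages need reconciling too.

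**Conclusion.** The point holds as an internal inconsistency with consequences for AE data. The 14.4 window and the 14.5 death clause name Vigil only. They leave Group B subjects who do not cross over without an end date, and in Group A subjects with about 4 to 10 doses they can close before on-study chemotherapy ends. The size runs from 128 days at 4 doses to 2 days at 10, and nil at 11 or 12. These figures assume no delays, 12 full chemotherapy cycles and chemotherapy continuing after the last Vigil dose; progression or early stopping would shrink them. The 158-day shortfall is the extreme case and includes a 30-day tail after treatment. Observation time becomes unequal between and within arms, with a direction of bias that depends on dose counts and on how sites read 14.4. It should be corrected; it does not touch the primary PFS analysis.

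**What to change.** - **Protocol 14.4 and 14.5:** in both arms, end AE recording and death reporting 30 days after the last dose of any study treatment (Vigil, irinotecan or temozolomide). Leave the open-ended duty to report all SAEs as it is.
- **Cross-over:** record AEs during cross-over Vigil up to 30 days after its last dose, but assign events from the first cross-over dose onward to a separate period and summarise them apart from the randomised comparison. Otherwise a common anchor would lengthen observation for some of Group B only.
- **Protocol 14.1:** refer to 14.4 for the start and end of recording, without narrowing the present commitment during treatment.
- **SAP 10.3:** redefine treatment-emergent events on the same window, and make SAP 13.2 consistent with it.

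A common anchor removes the inequality that the recording rule creates. It does not remove differences in time on treatment, which should be kept in mind when crude percentages are read.

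The cost is wording in the protocol and SAP, a derived flag for the cross-over period, and somewhat more AE data entry. No treatment or visit changes.
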